4.0 Study Objectives, Design and Procedures

4.1 Primary Study Objective

The primary objective of Study M15-997 is to investigate long-term safety and tolerability of risankizumab in subjects with psoriasis who have completed one of the preceding Phase 2/3 studies.

[figure not shown]
The secondary objective of Study M15-997 is to investigate the long-term efficacy of risankizumab in the treatment of psoriasis.

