10.0 Efficacy Analysis

10.1 General Considerations

The efficacy analysis will be performed for each population except the ALL_RZB Population. The efficacy analysis will use the data from this study and preceding study after subjects started to take risankizumab. The BL values (baseline values from the

preceding studies) will be used to determine responses and changes in the efficacy variables.

Continuous variables will be summarized by the number of observations, mean, standard deviation, median, minimum, maximum, 25th and 75th percentiles, as well as the 95% confidence intervals (CIs) of the mean values. Categorical variables will be summarized by counts and percentages, as well as the 95% CIs of the percentages. No statistical tests will be performed in this study.

Missing data will be imputed using the following methods for the efficacy analyses:

- Last Observation Carried Forward (LOCF): The LOCF analyses will use the last observed non-missing evaluation (last completed non-missing evaluation, from composite endpoint) from the previous visit within the particular period for efficacy measures assessed to impute missing data at later visits in the same period. Baseline efficacy evaluations will not be carried forward. Of note, post-baseline observations from Part A1 in Study 1311.4 can be carried forward to ITT_A2 subjects from ARM 1 since treatment is the same.
- As-Observed Cases (OC): The as-observed analysis will not impute values for missing evaluations, and thus a subject who does not have an evaluation on a scheduled visit will be excluded from the as-observed analysis for that visit.

LOCF will be used as the primary imputation method and OC will be used as sensitivity analysis for both categorical variables and continuous variables. Both LOCF and OC will not include values after discontinuation of study drug.

All endpoints will be analyzed up to the last visit with at least one subject has observed measurements of that variable, by the time of the interim data cutoff.

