The number and percentage of subjects experiencing treatment-emergent adverse events will be summarized for the following adverse event categories:

- Any AE
- Any AE that was assessed as related to study drug by the investigator
- Any severe AE
- Any serious AE
- Any serious AE that was assessed as related to study drug by the investigator
- Any AE leading to discontinuation of study drug
- Any AE leading to death
- Any deaths
- Areas of Safety Interest
- Any COVID-19 Related AE

2. Adverse Events by System Organ Class and Preferred Term

TEAEs will also be summarized and presented using primary Medical Dictionary for Regulatory Activities (MedDRA) system organ classes (SOCs) and preferred terms (PTs). The SOCs will be presented in alphabetical order, and the PTs will be presented in alphabetical order within each SOC.

Subjects reporting more than one adverse event for a given MedDRA preferred term will be counted only once for that term (most severe incident for the severity tables and most related incident for the relationship tables). Subjects reporting more than one type of adverse event within a SOC will be counted only once for that SOC. Subjects reporting more than one type of adverse event will be counted only once in the overall total.

In addition, the number and percentage of adverse events with causal relationship between the events and the study drug will be summarized using the same conventions described above.

3. Adverse Events by Maximum Severity

The severity grading of AEs follows Rheumatology Common Toxicity Criteria (RCTC).

- Grade 1 – mild
- Grade 2 – moderate
- Grade 3 – severe
- Grade 4 – life threatening

Adverse events will also be summarized by maximum severity. If a subject has an adverse event with unknown severity, then the subject will be counted in the severity category of "unknown," even if the subject has another occurrence of the same event with a severity present. The only exception is if the subject has another occurrence of the same adverse event with the most extreme severity – ("Life-threatening"). In this case, the subject will be counted under the "Life-threatening" category.

4. Adverse Events by Maximum Relationship

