Serious Infections	Serious AEs in the Infections and Infestations SOC	
Active Tuberculosis	Active Tuberculosis CMQ (code 80000188)	
Opportunistic Infections excluding tuberculosis and herpes zoster	Opportunistic infection excluding tuberculosis and herpes zoster CMQ (code 80000189)	
Injection Site Reactions	Narrow	Injection site reaction CMQ (code 80000019)
Malignancies	Narrow	Malignant tumours (SMQ 20000194)
Non-melanoma Skin Cancer (NMSC)	Broad	Skin malignant tumours (SMQ 20000204) excluding terms identified by the Melanoma CMQ (code 80000119)
Malignant Tumours excluding NMSC	'Malignant Tumours excluding NMSC' is identified by the 'Malignant Tumours' search excluding terms identified by the 'Non-melanoma skin cancer (NMSC)' search.	
Hypersensitivity	Narrow	Hypersensitivity (SMQ 20000214)
Serious hypersensitivity reactions	Narrow	Serious AEs in the Hypersensitivity (SMQ 20000214)
Adjudicated Anaphylactic Reaction*	Adjudicated terms will be identified using SDTM data (e.g., CE and PR domains).	
Hepatic Events	Broad	Hepatic failure, fibrosis and cirrhosis and other liver damage-related conditions (SMQ 20000013)
	Broad	Hepatitis, non-infectious (SMQ 20000010)
	Broad	Cholestasis and jaundice of hepatic origin (SMQ 20000009)
	Broad	Liver related investigations, signs and symptoms (SMQ 20000008)
	Narrow	Liver-related coagulation and bleeding disturbances (SMQ 20000015)

* Events will be identified for adjudication by Anaphylactic Reaction SMQ Broad search as specified in the RISA AAC Charter.

Adverse Event per 100 Patient-Years of Exposure

Adverse events occurring during the analysis period for each population will be presented by event rate per 100 patient-years. These will be presented for any TEAEs, serious adverse events, Areas of Special Interest.

AEs per 100 patient-years of exposure is defined as the number of AEs divided by the total exposure in 100 patient-years. Note that one event per preferred term per day per subject will be counted in the calculation of the number of AEs (i.e., a preferred term will not be counted twice on the same day for the same subject). See the calculation method below.

$$100 \times \frac{\text{Number of TEAEs}}{\text{Total Patient Years}}$$

where total patient years is defined as the sum of the study drug exposure (defined as date of last dose – date of first dose + 140 days (5 half-lives)) of all subjects normalized by 365.25, and rounded to one decimal place.

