Program Source Code: /[name]/SDA/ABBV-066/Psoriasis/CSR/M15-997/G/14.3/PCMS_RUN/s1311_31_aesi.sas

Table 14.3__2
Subjects with Treatment-Emergent AESI
(RZB Population)

Category MEDDRA 20.0 Preferred Term	RZB (N=) n (%)
<hr/>	
Subjects with:	
Fungal Infections	
...	XXX (XX.X)
...	XXX (XX.X)
Herpes Zoster	XXX (XX.X)
...	XXX (XX.X)

Program Source Code: /[name]/SDA/ABBV-066/Psoriasis/CSR/M15-997/G/14.3/PCMS_RUN/s1311_31_aesi.sas

Table 14.3__3
 Subjects with Treatment-Emergent Hypersensitivity by Subgroup
 (RZB Population)

Subgroup	RZB
Status	(N=)
Category	n (%)
MEDDRA 20.0 Preferred Term	
<hr/>	
Antidrug Antibody Positive Status (Yes, No)	
Yes	
Hypersensitivity	XXX (XX.X)
xxx	XXX (XX.X)
...	XXX (XX.X)
Anaphylactic Reaction	XXX (XX.X)
...	XXX (XX.X)
No	
Hypersensitivity	XXX (XX.X)
xxx	XXX (XX.X)

Program Source Code: /[name]/SDA/ABV-066/Psoriasis/CSR/M15-997/G/14.3/PCMS_RUN/s1311_31_aesi.sas

Table 14.3_4
 Subjects with Treatment-Emergent Injection Site Reaction by Subgroup
 (RZB Population)

Subgroup	RZB
Status	(N=)
MEDDRA 20.0 Preferred Term	n (%)
Antidrug Antibody Positive Status (Yes, No)	
Yes	XXX (XX.X)
xxx	XXX (XX.X)
No	XXX (XX.X)
xxx	XXX (XX.X)

Program Source Code: /[name]/SDA/ABV-066/Psoriasis/CSR/M15-997/G/14.3/PCMS_RUN/s1311_31_aesi.sas

Table 14.3__5
 Treatment-Emergent Adjudicated CV Adverse Events
 (RZB Population)

Category Sub-Category	RZB (N=) (PYS=) Events (E/100PY)
Subjects with:	
MACE	
Myocardial Infarction	XXX (XX.X)
...	XXX (XX.X)
Extended MACE	XXX (XX.X)
Myocardial Infarction	XXX (XX.X)
...	XXX (XX.X)
Other CV Events	XXX (XX.X)

Program Source Code: /[name]/SDA/ABBV-066/Psoriasis/CSR/M15-997/G/14.3/PCMS_RUN/s1311_31_aesipy.sas

Table 14.3__6
 Treatment-Emergent AESI
 (RZB Population)

Category MEDDRA 20.0 Preferred Term	RZB (N=) (PYS=) Events (E/100PY)
Subjects with:	
Fungal Infections	XXX (XX.X)
...	XXX (XX.X)
...	XXX (XX.X)
Herpes Zoster	XXX (XX.X)
...	XXX (XX.X)

Program Source Code: /[name]/SDA/ABBV-066/Psoriasis/CSR/M15-997/G/14.3/PCMS_RUN/s1311_31_aesipy.sas

Table 14.3__7
 Treatment-Emergent Hypersensitivity by Subgroup
 (RZB Population)

Subgroup	RZB
Status	(N=)
Category	(PYS=)
MEDDRA 20.0 Preferred Term	Events (E/100PY)
Antidrug Antibody Positive Status (Yes, No)	
Yes	
Hypersensitivity	XXX (XX.X)
Dermatitis	XXX (XX.X)
...	XXX (XX.X)
Anaphylactic Reaction	XXX (XX.X)
...	XXX (XX.X)

Program Source Code: /[name]/SDA/ABV-066/Psoriasis/CSR/M15-997/G/14.3/PCMS_RUN/s1311_31_aesipy.sas

Table 14.3__8

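### Exposure-adjusted safety rates, the core of the primary objective, are event-count rates with no confidence interval and no subject-level counterpart

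*SAP*

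**What the plan says.** SAP 4.1 puts safety first: "The primary objective of Study M15-997 is to investigate long-term safety and tolerability of risankizumab". Efficacy is secondary.

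For safety rates, SAP 11.2.1 says "Adverse events occurring during the analysis period for each population will be presented by event rate per 100 patient-years". It covers any TEAE, serious AEs and the areas of interest.
- **Numerator:** "AEs per 100 patient-years of exposure is defined as the number of AEs divided by the total exposure in 100 patient-years". The only de-duplication is that "one event per preferred term per day per subject will be counted in the calculation of the number of AEs".
- **Denominator:** the sum over subjects of "date of last dose – date of first dose + 140 days (5 half-lives"), divided by 365.25.
- **Subject-level companion:** "The number and percentage of subjects experiencing treatment-emergent adverse events will be summarized for the following adverse event categories". This is a crude percentage.
- **Layout:** the rate shells in SAP Appendix A have N and patient-years in the column header and one body column, "Events (E/100PY"), laid out as XXX (XX.X).

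For efficacy, SAP 10.1 says "Categorical variables will be summarized by counts and percentages, as well as the 95% CIs of the percentages", and gives means a 95% CI too. The same paragraph says that no tests will be done. Neither SAP section 11 nor protocol 8.1.5 plans an interval for any safety quantity.

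Protocol 8.1.5 asks for percentages and events per 100 patient-years for SAEs, deaths, AEs leading to discontinuation and AESIs. The list of rates in SAP 11.2.1 leaves out discontinuation AEs and gives deaths no rate of their own.

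**The concern.** Long-term safety here turns largely on rare outcomes, such as MACE, malignancy, active tuberculosis and adjudicated anaphylaxis (SAP Table 12). For these, the useful statement is how high a rate the data can exclude. An event-count rate without limits does not make that statement.

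There are three separate gaps:
- **No interval.** A zero or near-zero row shows no upper limit in any population, large or small.
- **No subject-level rate.** Repeats on other days, or under other preferred terms in the same area, all enter the numerator. The subject percentage avoids this but ignores follow-up time. Follow-up differs across populations: windows run to Week 304 for RZB (SAP Table 1) and to Week 252 for UST_RZB and FUM_RZB (SAP Table 10). It also differs within populations through early discontinuation.
- **Rounding.** At one decimal, a small non-zero rate prints as 0.0.

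**Working it through.** **The plan's own figure.** The documents give no precision target, expected safety rate or patient-year total. The only size figure is about 2200 entrants after 10% to 15% dropout. The stated enrolments (protocol 5.6.4) are about 2100 in four Phase 3 studies and 110 in 1311.13: 2210 × 0.90 = 1989 and 2210 × 0.85 = 1879. The rest would have to come from 1311.38 and M16-178, whose totals are not given. So 2200 can be neither reproduced nor called wrong. It is used below only as an input.

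**Patient-years per subject.** With the last dose at Week 252 and the 140-day tail, (252 × 7 + 140) / 365.25 = 1904 / 365.25 = 5.21. This is the maximum within the OLE. It assumes full completion and leaves out exposure in the preceding studies.

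**Zero events.** The exact two-sided 95% upper limit is −ln(0.025) / PY = 3.689 / PY. The sizes 30 to 100 and the 3 patient-years per subject are assumptions, because no population size is stated.

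| Subjects | PY at 5.21 each | Upper limit per 100 PY | Upper limit at 3 PY each |
|---|---|---|---|
| 30 | 156 | 2.36 | 4.10 |
| 50 | 261 | 1.42 | 2.46 |
| 100 | 521 | 0.71 | 1.23 |
| 2200 | 11,468 | 0.032 | 0.056 |

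Every row would print a rate of 0.0.

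**Rounding.** A rate below 0.05 per 100 PY prints as 0.0 in XX.X format. At 11,468 PY that means fewer than 0.05 × 11,468 / 100 = 5.7 events, so one to five events also print a rate of 0.0. Five events are 0.044 per 100 PY, exact 95% CI 0.014 to 0.102. The count beside the rate would show 5.

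**Events against subjects.** Take 50 subjects and 261 PY. Five events give 500 / 260.6 = 1.92 per 100 PY whether they come from five subjects or from one. Counted by subjects with an event, keeping the full person-time for simplicity:
- five subjects: 1.92 (0.62 to 4.48)
- one subject: 0.38 (0.01 to 2.14)

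**Why not a Poisson interval on the event counts.** Gamma-Poisson counts were simulated at an assumed 4 events per 100 PY, with between-subject frailty variance 2, 5 and 10. The expected count per subject is 0.04 × 5.21 = 0.209, so the variance inflation 1 + variance × 0.209 is 1.42, 2.04 and 3.09. Coverage of a nominal 95% Poisson interval fell to about 91%, 85% and 75% with 50 subjects, and to 90%, 84% and 74% with 2200. A larger population does not cure it.

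**The case against.** The best defence is that the design is descriptive and the raw material is on the page. The rate shells print N, patient-years and the event count, so a zero row sits under its own denominator. The event-rate shells for cardiovascular events, AESIs and hypersensitivity each have a subject n (%) companion. By-subject listings are planned for SAEs, deaths, discontinuations due to AEs and the areas of safety interest. Protocol 8.1.5 asks for no interval, so its absence breaches no commitment. Appendix A covers only non-standard tables, and the full table list is in a separate document.

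Much of this stands, and it rules out several stronger readings that a reader might infer:
- *That the tables hide the difference in information between populations.* They do not, because the denominators are printed.
- *That a rate driven by a few subjects would go unseen.* The subject counts and listings would show it.
- *That a particular fold-difference in precision between populations is established.* With zero events it is only the ratio of two denominators, and the documents give neither.
- *That event-count rates cannot carry a valid interval, or that the planned rates are wrong.* An interval that allows for clustering is possible, and nothing shows an incorrect rate.

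The defence does not supply the missing quantities. The percentages have no interval and are not exposure-adjusted, and the limits are left for the reader to derive. The no-testing rule is no reason to omit intervals, since SAP 10.1 plans efficacy intervals beside it. A separate table list might contain more, but the SAP methods text plans none.

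**Conclusion.** The concern holds as a gap in reporting, not as an error in the rates. The primary objective gets event-count rates without limits, while the secondary objective gets 95% CIs throughout, and no subject-level exposure-adjusted rate is planned.

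The consequence is largest for rare areas in small populations. At 5.21 patient-years per subject, a zero row is compatible with true rates up to 0.7 to 2.4 per 100 patient-years for 100 down to 30 subjects, against 0.03 for 2200. At 3 patient-years per subject the limits are 1.2 to 4.1 and 0.06. The small-population sizes, the 3 patient-years and the clustering parameters are assumptions. The absence of an interval, the event-based numerator and the one-decimal format are in the documents.

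The omission of separate event rates for deaths and of any rate for discontinuation AEs is a plain difference between protocol 8.1.5 and SAP 11.2.1.

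**What to change.** Amend SAP 11.2.1 and the rate shells before database lock:

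1. For SAEs, deaths, AEs leading to discontinuation and each Table 12 area, add the number of subjects with a first event per 100 patient-years. Censor person-time at the first event. Give an exact Poisson 95% CI, including the upper limit for zero rows, to at least two decimals.
2. Derive that person-time to match each population's TEAE period. Leave out the off-treatment part of the 1311.4 Part B gap that the TEAE rule excludes, and apply the data cut-off for subjects in Japan (SAP 9.0, 11.1 and 11.2.1).
3. Add events per 100 patient-years for deaths and discontinuation AEs, as protocol 8.1.5 requires.
4. Keep the planned event rates, but put no plain Poisson interval on them. If they are to have an interval, use a variance that allows for within-subject clustering.

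The cost is additional programming and table columns. Censored person-time has to be derived for each outcome in each population, so this is more than a formatting change, but the event and dosing dates are already held. The intervals are descriptive and do not conflict with the decision to run no tests.

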Subjects with a positive QuantiFERON[®]-test or a positive purified protein derivative (PPD) skin test for tuberculosis (TB) must fulfill entry criteria as specified in Section 5.2.2.

IL-23 inhibition is not known to increase the risk of TB infection or impair the response to TB infection in animal models.^{10,11} Thus, low risk subjects with positive QuantiFERON TB testing are not required to be treated with anti-tuberculosis therapy prior to receiving risankizumab, but should be carefully monitored for any sign of TB reactivation. Absence of TB reactivation, despite not receiving anti-tuberculosis prophylaxis will provide important information in humans as to whether TB testing is required prior to treatment with risankizumab.¹²

There have been post marketing reports of the rapid appearance of multiple cutaneous squamous cell carcinomas in patients receiving ustekinumab, anti-IL12/23 mAb who had

pre-existing risk factors for developing NMSC.¹³ Patients with moderate to severe PsO generally have risk factors for development of NMSC. In the completed studies to date, risankizumab has not been associated with an increased risk of malignancies but the risk with long-term therapy is not known.

Increases in the incidence rate of major adverse cardiovascular events (MACE) including myocardial infarction, cerebrovascular accident, and cardiovascular death, reported in the 12 week controlled portions of the clinical trials with anti-IL-12/23 agents, such as ustekinumab, have not been observed in longer term studies.¹⁴

In order to recognize any safety signals as early as possible, an independent Data Monitoring Committee (DMC) has been monitoring unblinded data from all studies where subjects are receiving risankizumab. As the sponsor has comprehensive safety monitoring measures in place to enable signal detection in open label studies, monitoring by the independent DMC will no longer be in effect for this open-label study. Routine pharmacovigilance surveillance will continue to be conducted.

An independent adjudication committee will be adjudicating all observed cardio- and cerebro-vascular events including major adverse cardiovascular events (MACE) in a blinded manner.

In conclusion, the benefit-risk profile of risankizumab is considered appropriate for allowing subjects to continue therapy under this long-term extension study.

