5.6.4 Selection of Doses in the Study

Risankizumab is currently in Phase 3 development for treatment of subjects with moderate to severe chronic plaque psoriasis. Four Phase 3 studies are currently ongoing, planning to enroll approximately 2100 subjects, and evaluating risankizumab dose of 150 mg administered at Week 0, 4 and thereafter E12W. Subjects from these ongoing Phase 3 studies will enter in the current study. Hence, the 150 mg dose administered E12W is selected for this study, so the subjects will continue to receive the same dose as in preceding Phase 3 studies to establish the long-term safety and efficacy of risankizumab. In Japanese Phase 2/3 Protocol 1311.38 some subjects (N = 56) will be treated with risankizumab 75 mg E12W dose. As risankizumab has been well tolerated in the completed and ongoing studies, and based on preliminary PK results indicating no clinically meaningful difference in exposure between Japanese and Caucasian subjects, (approximately 30% higher exposure in Japanese subjects compared to Caucasian subjects) AbbVie considers it appropriate to investigate 150 mg E12W dosing paradigm in these Japanese subjects.

Subjects currently enrolled in BI clinical Trial 1311.13 will also be offered the opportunity to continue receiving treatment for chronic plaque psoriasis with risankizumab in Study M15-997. One-hundred and ten subjects were enrolled in this trial and were treated with risankizumab 90 mg SC E12W with the option to increase the dose to 180 mg if there was evidence of lack of response.

Preliminary results from the pivotal Phase 3 studies support the clinical benefit of the 150 mg dose of risankizumab in subjects with moderate to severe plaque psoriasis. Approximately 1300 subjects received treatment with risankizumab 150 mg SC and all four pivotal trials achieved their co-primary endpoints which were defined as achievement

of $\geq 90\%$ reduction from baseline PASI score (PASI 90) at Week 16 and achievement of a sPGA score of clear or almost clear at Week 16.

Subjects treated with risankizumab experienced substantial skin clearance and clinical improvement in the extent and severity of plaque. Across the four pivotal studies, the proportion of subjects with PASI 90, sPGA score of clear or almost clear, and PASI 100 at Week 16 ranged from 72 – 75%, 84 – 88%, and 36 – 51%, respectively.

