4.2 Design Diagram

This is a Phase 3, single-arm, multicenter, OLE study designed to investigate the long term safety and efficacy of risankizumab 150 mg E12W in the treatment of moderate to severe chronic plaque psoriasis. Approximately 2200 subjects who meet the entry criteria are planned to be enrolled in this study, rolling over from the preceding Studies 1311.3, 1311.4, 1311.13, 1311.28, 1311.30, 1311.38, and M16-178 (Phase 2/3, randomized clinical studies in subjects with moderate to severe chronic plaque psoriasis, conducted by Boehringer Ingelheim or AbbVie).

All subjects need to complete one of the preceding Phase 2/3 psoriasis studies. The subject preferably has the Baseline visit of Study M15-997 on the same day of the completion visit of the preceding study; however, the Baseline visit can be delayed up to 8 weeks if needed. All subjects will be administered 150 mg risankizumab s.c. at the Baseline visit, and from the Baseline visit onwards, risankizumab will be administered subcutaneously E12W during the study. Study visits for dosing, efficacy and safety assessments will be performed E12W starting from Baseline until the Week 156 visit. After this visit until the End of Treatment (EOT) visit at Week 252, study visits will be performed E24W. The schematic of the study is shown in [Figure 1](#).

Figure 1. Study Schematic

There is a ± 7 days visit window for study visits. Every effort will be made to bring subjects back to their original scheduled visit (calculated from Baseline) if they are out of the visit window. Subjects who discontinue study drug treatment early will need to attend an early EOT visit ideally within 2 weeks after the decision and preferably prior to the administration of any new therapies.

All subjects, including those that prematurely discontinued study drug treatment, will return to the clinic for an End of Observation Visit (EOO) 20 weeks after their last administered dose of risankizumab. Study completion is defined as a subject having completed the EOO visit.

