4.3 Sample Size

The sample size is determined by the completion of preceding studies and the consenting for the extension.

Multiple clinical studies will be rolling into this OLE study. Eligible subjects from Studies 1311.3, 1311.4, 1311.13 (extension study of 1311.2), 1311.28, 1311.30, 1311.38, and M16-178 will be offered participation in this OLE study at their respective or referring sites. The check for subject eligibility will be based upon a successful completion of the preceding study, signing the informed consent for this study, and the other inclusion and exclusion criteria.

A 10% to 15% dropout rate from preceding studies is expected, leaving approximately 2200 subjects to be entered in this study.

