6.0 Analysis Conventions

Since this is an open-label continuation study, no statistical test will be conducted. Summary statistics will be provided. Data from preceding studies will be integrated with data from this study in the summaries.

Definition of Baseline

For this study, the following two types of baseline values are defined.

1. Preceding Study Baseline Value (BL): These values represent the baseline values of preceding studies, that is, the last non-missing values on or before the date of the first dose of study drug in the preceding study. For vital sign assessments, only assessments prior to first dose time will be considered, since vital signs are to be assessed both pre- and post-dose in some visits. The efficacy analysis based on RZB, RZB_NL, Retreatment, UST_RZB, ADA_RZB, FUM_RZB, and RZB_Japan populations will use these baseline values. These baseline values will be referred to as "BL" in this document. Unless otherwise specified, this will be the "baseline" for analysis.
2. RZB baseline value (BL_RZB): These values are the last non-missing values on or before the date of the first dose of risankizumab in the preceding study or Study M15-997. For vital sign assessments, only assessments prior to first dose time will be considered, since vital signs are to be assessed both pre- and post-dose in some visits. These values will be referred to as BL_RZB in this document. BL_RZB will be used for safety analyses in all populations.

Definition of Final Observation (Applicable to Safety Analyses)

Final observation in the entire study is defined as the last non-missing observation collected within 140 days after the last dose of risankizumab.

Definition of Rx Days (Days Relative to the Date of First Dose of Study Drug)

Rx days are calculated for each time point relative to the date of first dose of risankizumab in the corresponding study period. They are defined as the number of days between the day of the first dose of risankizumab and the specific time point. Rx days are negative values when the time point of interest is prior to the first risankizumab dose day. Rx days are positive values when the time point of interest is on or after the first risankizumab dose day. The day of the first dose of risankizumab is defined as Rx Day 1, while the day prior to the first risankizumab dose is defined as Rx Day -1 (there is no Rx Day 0).

Definition of Analysis Windows

All time points and corresponding time windows are defined based on Rx Days.

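### Adverse event rates are planned only as one cumulative figure per population, so the planned AE summaries cannot show whether the risk of serious events changes with time on risankizumab

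*SAP*

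**What the plan says.** SAP 4.1: "The primary objective of Study M15-997 is to investigate long-term safety and tolerability of risankizumab". For malignancy, Protocol 3.2 adds that "the risk with long-term therapy is not known".

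SAP 11.2.1 covers adverse event rates as follows: "Adverse events occurring during the analysis period for each population will be presented by event rate per 100 patient-years". The rate is 100 times the number of treatment-emergent events divided by total patient-years. Each subject contributes the time from first to last dose plus 140 days. Counts, percentages, severity and relationship tables in the same section also run over the whole period.

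Exposure is summarised as total duration only (SAP 9.0). The safety subgroups are Japan and anti-drug antibody status (SAP 11.6). The study is descriptive: "Since this is an open-label continuation study, no statistical test will be conducted" (SAP 6.0).

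Every analysis population requires a risankizumab dose in M15-997 (SAP 5.0). Protocol 5.2.2 keeps out anyone who left the preceding study early (criterion 1). It also keeps out anyone who developed a malignancy in that study, apart from treated basal or squamous cell skin cancer and cervical carcinoma in situ (criterion 5). Exposure and treatment-emergent events nevertheless count from the first risankizumab dose, which for many subjects lies in the preceding study.

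**The concern.** A long-term extension exists largely to learn whether risk changes as exposure accumulates. Malignancy, MACE and serious infection are the events for which that matters most. One ratio of events to patient-years averages early and late time, so it looks the same whether late risk is higher, lower or unchanged.

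The pooled figure has a second weakness. Risankizumab time in the preceding study enters the denominator. However, subjects who died in that study, stopped early because of an adverse event, or developed most kinds of non-NMSC malignancy could not enter M15-997. For those events the early time is nearly event-free by selection and pulls the pooled rate down.

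**Working it through.** **1. Which planned safety outputs show time?**

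| Output | SAP | By time on drug? |
|---|---|---|
| TEAE counts and percentages | 11.2.1 | No |
| AE rate per 100 patient-years | 11.2.1 | No |
| Deaths, SAEs, areas of safety interest: listings | 11.2.1, 11.2.2 | No interval patient-years |
| Potentially clinically important laboratory values, liver categories | 11.3.2 | No |
| Laboratory and vital-sign changes | 11.3.2, 11.4.2 | Yes, by visit, but not for ALL_RZB or Retreatment (11.1) |
| Exposure | 9.0 | Total duration only |

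Neither document plans interval AE rates, a time-to-event curve or a hazard estimate.

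**2. The plan's own figure.** SAP 4.2: "Approximately 2200 subjects who meet the entry criteria are planned to be enrolled in this study". SAP 4.3: "A 10% to 15% dropout rate from preceding studies is expected". The implied feeder total is 2200/0.90 = 2445 to 2200/0.85 = 2589 (rounded up). Protocol 5.6.4 gives about 2100 for the four Phase 3 studies and 110 for Study 1311.13, or 2210 together. The other 235 to 379 would come from 1311.38 and M16-178, whose totals are not given. The 2200 can be neither confirmed nor refuted, and the point does not depend on it. No event rate or precision target is stated.

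**3. Length of exposure.** A subject first dosed in the extension has up to 252 × 7 + 140 = 1904 days, or 1904/365.25 = 5.2 years. In the RZB Population the windows run to Week 304. Adding 20 weeks gives 324 weeks, and 324 × 7/365.25 = 6.2 years.

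**4. Person-time in the extension.** 2200 × 1904/365.25 = 11,468 patient-years with no dropout. It is 10,063 at an assumed 5% annual dropout and 8,824 at 10%.

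**5. Can the pooled rate tell risk patterns apart?** Assume a pooled 0.5 per 100 patient-years and no dropout: 0.005 × 11,468 = 57 events, exact Poisson 95% CI 0.38 to 0.65 (the SAP plans no CI for this rate). Patient-years are 2200 in each of years 1 to 5 and 468 afterwards, with the year-5 rate continuing. In the tripling pattern, yearly rates are in the ratio 1 : 1.5 : 2 : 2.5 : 3. The falling pattern reverses this. "Late" below means after year 3 and "early" means years 1 and 2, both counted in the extension.

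| Pattern | Planned output | Years 1 to 5, per 100 PY | Late/early ratio (95% CI) |
|---|---|---|---|
| Flat | 0.5 | 0.50 throughout | 1.00 (0.56–1.78) |
| Tripling | 0.5 | 0.24, 0.37, 0.49, 0.61, 0.73 | 2.22 (1.18–4.18) |
| Falling to a third | 0.5 | 0.77, 0.64, 0.51, 0.38, 0.26 | 0.45 (0.24–0.82) |

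For the tripling row, late events are 13.5 + 16.2 + 3.4 = 33.1 over 4868 patient-years. Early events are 5.4 + 8.1 = 13.5 over 4400. The log-ratio standard error is √(1/33.1 + 1/13.5) = 0.32.

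**6. How much would a split detect?** For the tripling pattern, over 0% to 10% annual dropout, the chance that the 95% CI for the ratio excludes 1 is 43–48% at a pooled 0.3 per 100 patient-years, 63–69% at 0.5 and 90–94% at 1.0.

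**7. Dilution by selected preceding-study time.** A full-term RZB Population subject has 304 − 252 = 52 weeks before the extension, and 52/324 = 16% of person-time. The share is larger for a subject who stops early in the extension and zero for one first dosed there. Take the extreme case in which selection removes every such event from those 52 weeks and the true rate is constant at 0.5. The pooled rate becomes 0.5 × 272/324 = 0.42. A table by year since first risankizumab dose would show about 0 in year 1 and 0.5 later, an apparent rise with no change in risk.

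**The case against.** Much of the other side's case stands.

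- A reader might infer that no safety data are shown over time. That is too broad: laboratory and vital-sign changes are planned by visit, and local tolerability has visit windows. The gap concerns adverse events.
- A reader might infer that the SAP assumes a constant hazard. It does not. Events over patient-years is a descriptive average, with no test or CI attached.
- A reader might infer that the pooled rate only repeats what short studies give. It does not, because the extension alone supplies roughly 8,800 to 11,500 patient-years under 0% to 10% annual dropout.
- Listings and the September 2017 and November 2021 interim cut-offs give some view of timing. Listings lack patient-years per interval, however, and the cut-offs are cumulative calendar snapshots. Neither yields a rate by time on drug.
- The list of tables and the Product Safety SAP are separate documents and were not available. An interval analysis may exist there.
- Yearly rates for rare events are imprecise. With no control arm, a trend may also reflect ageing, COVID-19 calendar time or selective dropout. This limits interpretation but does not justify leaving the pattern undisplayed.
- A split by year since first risankizumab dose would mislead, as step 7 shows. This objection stands in full and determines the form of the fix.

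**Conclusion.** The point holds for adverse events and for the summaries that this protocol and SAP plan. One cumulative rate per population cannot show whether the risk of serious events changes over about 5 to 6 years, and that question is central to the primary objective. The dates needed to answer it are already collected, so the gap is in the planned output and not in the data.

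The conclusion that the pooled rate cannot separate the three patterns needs no assumed event rate. The sizes shown do: pooled rates of 0.3 to 1.0 per 100 patient-years, annual dropout of 0% to 10%, and a threefold change chosen for illustration. Nothing in the documents suggests that risk actually rises. The 16% applies to a full-term RZB Population subject, and the drop from 0.5 to 0.42 is the extreme case of complete selection.

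**What to change.** Add to SAP 11.2.1 one descriptive table for ALL_RZB, by year since the first dose in M15-997 (0–1, 1–2, 2–3, 3–4, more than 4). For SAEs, serious infections, MACE, malignancies excluding NMSC, and NMSC, give in each interval:

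- events and subjects with a first event;
- number at risk and patient-years;
- events per 100 patient-years with 95% CI.

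Show preceding-study risankizumab time as a separate row. Its footnote should say that this time is selected for completers and for mostly malignancy-free subjects, and must not be read as an early-risk baseline. If years since first risankizumab dose are also shown, count person-time only from entry to M15-997 (delayed entry).

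The table should state that yearly estimates are imprecise for rare events and that a trend may reflect ageing, COVID-19 calendar time or selective dropout. If the Product Safety SAP or the separate table list already contains such an analysis, a cross-reference is enough.

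The cost is a paragraph of SAP text and one table. It needs no new data and no test.
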